6.3.3. Exploratory efficacy analysis

Evaluation of LTBP4 and osteopontin genotype

In order to determine whether the effects of givinostat versus placebo are related to the type of Mutation Exon or the LTBP4 and Osteopontin (i.e. SPP1) genotypes, three further subgroups of subjects will be defined: Mutation Exon (Exon 45, Prior to exon 45, Post-exon 45), LTBP4 (IAMM, VTTT, Other, VTTT+Other) and SPP1 (TT, GT, GG, GG+GT).

The number and proportion of patients in each subgroup will be summarized as appropriate. Further analyses are described in Section 6.5.

Evaluation of the functional test velocity

Velocity for each functional test will be computed at each visit from the following variables:

- 4-Stair ascent duration
- Rising from floor duration
- 10-Metre Walk/Run test duration

For patients with missing data TFT data due to lack of ability to perform the test, their velocity will be set equal to zero.

Velocity to 4-Stair Climb will be calculated according to the following formulas:

$$Velocity_{4-Stair\ Climb} = \frac{4}{time\ to\ climb\ 4\ stair}$$

Sponsor: ITALFARMACO
Protocol: DSC/15/2357/53

The velocity will be set to zero for patients who don't attempt the test with reason "Unable to physically perform the test" or for patients with the lowest grade (1) for the 4 Stair Climb test.

The absolute value of velocity to 4-Stair Climb and change versus baseline, at each time point, will be summarized as continuous variables using descriptive statistics.

To make best use of repeated intra-subject evaluations of 4-Stair Climb velocity, the absolute change from baseline to visits 8, 9 10 and 11 (months 3, 6, 9 and 12) will be analyzed using mixed model repeated measures (MMRM) analysis. Fixed effect class terms will be included for treatment, visit, visit x treatment interaction and concomitant steroid use at baseline; baseline value will be included as a covariate. An unstructured covariance matrix will be used to model the within-subject error. LSmeans and SEs and also the difference in LSmeans between treatments will be extracted by visit; SEs, 2-sided 95% CIs and 2-sided p-values will also be extracted for the difference in LSmeans. The principal focus of inference will be the results at visit 11 (month 12).

Velocity to walk/run 10 m will be calculated according to the following formula:

$$Velocity_{walk/run \ 10 \ m} = \frac{10}{time \ to \ walk/run \ 10 \ m}$$

Velocity to rise from floor will be calculated according to the following formula:

$$Velocity_{Rise\ from\ floor} = \frac{1}{time\ to\ rise\ from\ floor}$$

Velocity to rise from floor and Velocity to walk/run 10 m will be analysed in the same manner as Velocity to 4-Stair Climb.

Moreover, to aid interpretation, if there will be patients unable to perform the test (or with the lowest grade) the variance-covariance matrix for LSmean estimates will be extracted by visit. The LSmeans will be reciprocated by visit to present TFT results back on the original scale. The difference in the reciprocated LSmeans (ie. $\Delta = LSmean_d^{-1} - LSmean_p^{-1}$) will be presented along with the associated 95% CI; for the latter the variance of Δ is required. This will be estimated using the variance-covariance matrix computed vis Taylor's expansion and the Delta rule as

$$Var(\Delta) = \frac{Var(LSmean_d)}{(LSmean_d)^4} - 2\frac{Cov(LSmean_d, LSmean_p)}{(LSmean_d)^2(LSmean_p)^2} + \frac{Var(LSmean_p)}{\left(LSmean_p\right)^4}$$

The CI for the difference in the reciprocated LSmeans is then given by

$$\Delta \pm t_{0.975,df} \cdot \sqrt{Var(\Delta)}$$

Sponsor: ITALFARMACO Protocol: DSC/15/2357/53

there $t_{0.975,df}$ is the 97.5th percentile of the t-distribution with df degrees of freedom where this is taken from the MMRM analysis.

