#### 4 INTRODUCTION

## 4.1 Background on Becker Muscular Dystrophy

Dystrophinopathies include a spectrum of muscle diseases caused by pathogenic variants in the *DMD* gene, which encodes the protein dystrophin. The mild end of the spectrum includes the phenotypes of asymptomatic increase in the serum concentration of creatine phosphokinase (CK) and muscle cramps with myoglobinuria. The severe end includes progressive muscle diseases that are classified as Duchenne/Becker muscular dystrophy when skeletal muscle is primarily affected and as DMD-associated dilated cardiomyopathy (DCM) when the heart is primarily affected (*Darras et al. 2000*). The BMD phenotype occurs when some dystrophin is produced due to deletions or duplications that juxtapose inframe exons, some splicing variants, and most non-truncating single-base changes that result in translation of a protein product with intact N and C termini. The shorter-than-normal dystrophin protein molecule, which retains partial function, produces the milder Becker phenotype (*Deburgrave et al. 2007*). Becker muscular dystrophy (BMD) occurs in approximately 1 in 30,000 male births (*Hedge et al. 2008*).

Symptoms of Becker muscular dystrophy usually begin in the teens or late twenties. Initial symptoms may include cramping and reduced endurance during exercise. Muscle gradually deteriorates in the hips, pelvis, thighs and shoulders leading to walking on toes with the stomach forward. Shortening of muscle fibers can result in the inability to move certain muscles (contractures). The progression of BMD is slower and more variable than Duchenne Muscular Dystrophy (DMD) but usually results in the need for a wheelchair.

Subclinical or clinical cardiac involvement is present in approximately 90% of individuals with BMD and is characterized by replacement of myocardium with connective tissue or fat. The left ventricular walls are most extensively affected, sparing the right ventricle and the atrium. Typical initial manifestations of cardiac involvement are sinus tachycardia, tall R1 in V1, prominent Q in I, aVL, V6 or in II, III, and aVF, increased QT dispersion and possibly autonomic dysfunction. Initially, echocardiography is normal or shows regional wall motion abnormalities in areas of fibrosis. With spreading of fibrosis, left ventricular dysfunction and

17 June 2020 Page 28 of 110

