In conclusion, ITF2357 appeared to be reasonably well tolerated at the tested doses in healthy volunteers or patients, where dose-related platelets count reductions and diarrhea were the most frequently reported AEs.

Concerning the clinical experience in dystrophinopathies, a phase II clinical trial (DSC/11/2357/43) has been conducted to evaluate the safety and the potential of ITF2357 as a treatment for DMD (*Bettica et al. 2016*). DSC/11/2357/43 was an open label 2-part, Phase II study in ambulatory children aged ≥ 7 to 10. Part 1 was a dose escalation study to identify the Maximum Tolerated Dose (MTD) and recommend the dose for Part II (12 months). The primary objective of the study was to confirm in humans that ITF2357 can counteract the histological signs of the disease by evaluating the drug's effects comparing baseline and end of treatment muscle biopsies (brachial biceps). The primary endpoint was the change of Muscle Fiber Area Fraction (MFAF) after 12 months of treatment. Additional histological parameters assessed as secondary endpoints were cross-sectional area (CSA), necrosis, hypercontracted fibers, fatty replacement and fibrosis. Secondary endpoints were change in muscular function after 12 months of treatment based on the 6 Minute Walking Test (6MWT), North Star Ambulatory Assessment (NSAA) and Performance Upper Limb (PUL).

MFAF increased in all children with a mean relative increase of 29.1% (p<0.0001). Endomysial and perimysial fibrosis decreased in all children with a mean relative decrease in total fibrosis of 27.4% (p<0.0001). Moreover, significant improvements of histological features were observed with reduction of necrotic and hypercontracted fiber number, as well as decrease of fat tissue replacement. MFAF increased due to a homogeneous increment of the CSA value of all fibers with a mean change of 865.27±555.35 μm². Change in 6MWT distance, NSAA total score, time to stand from floor and PUL were -24.6±36.11 meters (mean±SD), -2.5±2.85 points, 0.72±1.36 seconds and -0.2±2.69, respectively.

The study protocol was amended and an extension phase is ongoing. The extension will allow the evaluation of the safety and tolerability of long-term administration of ITF2357 (for up to 4 years of treatment) and to evaluate the effect of treatment on muscle function.

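### SAP 6.3.3 inverts least-squares means of change in velocity to show timed tests in seconds, but one over a change in velocity is not a test time

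*SAP*

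**What the plan says.** SAP 6.3.3 defines velocity as 4/time for the stair climb, 10/time for the 10 m walk/run and 1/time for rising from the floor. Patients unable to perform a test get velocity zero. For the stair climb, "the absolute change from baseline to visits 8, 9 10 and 11 (months 3, 6, 9 and 12) will be analyzed using mixed model" for repeated measures, with baseline velocity as a covariate, and "LSmeans and SEs and also the difference in LSmeans between treatments will be extracted by visit". The other tests follow: "Velocity to rise from floor and Velocity to walk/run 10 m will be analysed in the same manner as Velocity to 4-Stair Climb". The endpoint table in SAP section 2 and the subgroup list in SAP 6.5 also name the quantity as change in velocity.

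The SAP then adds a presentation step, to be used "if there will be patients unable to perform the test (or with the lowest grade"). In that case, "The LSmeans will be reciprocated by visit to present TFT results back on the original scale". The reported contrast is Δ = 1/LSmean_d − 1/LSmean_p (d for drug, p for placebo), with a delta-method variance and a 95% CI.

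**The concern.** The model's LS means are mean changes in velocity. Turning velocity back into time needs the velocity itself, that is, baseline plus change. The SAP has no step that adds baseline back, and it describes no model of the velocity level; levels are only summarised descriptively.

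The step is there to help readers. The secondary timed-test analysis in SAP 6.3.2.5 is in seconds, but a patient who cannot do the test has no time to contribute. The back-transformed velocity is the planned way to give a result in time units that includes such patients. As written, it would give negative or very large figures with a formal confidence interval, and in some cases would show the treatment effect in the wrong direction.

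**Working it through.** The plan states no figure to reproduce, so the check is algebra plus illustration. The documents contain no velocity data: **all baselines, changes and SEs below are assumed**, and covariance is taken as 0.

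**1. What is inverted.** Let b be baseline velocity, and c_d and c_p the LS mean changes. The plan computes Δ = 1/c_d − 1/c_p. The coherent quantity is k/(b + c_d) − k/(b + c_p), with k = 4, 1 or 10. For given changes, b does not enter the plan's figure. Each reciprocal is undefined at c = 0 and negative for any decline. When c_d and c_p have the same sign, Δ keeps the right direction. When c_d > 0 > c_p, Δ is positive, which reads as givinostat slower although it is faster.

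**2. The variance formula.** As a formula for a difference of two reciprocals, the printed expression is right. For level velocities 0.19 and 0.17 with SEs 0.008 and 0.011, it gives SE 0.440; simulation with 2,000,000 draws gives 0.447. The fault is the input: with changes inserted, the denominators are c⁴ and the variance blows up as c nears zero.

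**3. Four-stair example (stairs/s; k = 4).**

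| Changes (givinostat, placebo) | Plan's Δ, any baseline | Coherent, b = 0.5 | b = 1.0 | b = 2.0 |
|---|---|---|---|---|
| −0.05, −0.10 | 1/(−0.05) − 1/(−0.10) = −10 | −1.11 s | −0.23 s | −0.05 s |
| +0.02, −0.02 | 1/0.02 − 1/(−0.02) = +100 | −0.64 s | −0.16 s | −0.04 s |

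For example, the row 1 entry at b = 1.0 is 4 × (1/0.95 − 1/0.90) = −0.23 s.

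SE for row 1 with assumed SEs 0.04 and 0.056:
- Plan: √(0.04²/0.05⁴ + 0.056²/0.10⁴) = √(256 + 31.36) = 16.95.
- Coherent, b = 1.0: 4 × √(0.04²/0.95⁴ + 0.056²/0.90⁴) = 0.33 s.

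**4. Rise from floor (k = 1).** Assume a 5 s baseline (0.20/s), changes −0.01 and −0.03, and SEs 0.008 and 0.011.
- Plan: the two reciprocals are −100 and −33.3, so Δ = −66.7 (SE 80.9).
- Coherent: 1/0.19 = 5.26 s and 1/0.17 = 5.88 s, a difference of −0.62 s (SE 0.44).
- If givinostat instead improves by 0.005, the plan gives +233 (SE 320) and the coherent value is −1.00 s.

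**5. The constants 4 and 10.** This is a separate fault. At a velocity level of 0.95, the bare reciprocal is 1.05, but the times are 4/0.95 = 4.21 s for the stairs and 10/0.95 = 10.53 s for 10 m. Only rise from floor, defined as 1/time, comes back as a time.

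**6. How often changes sit near zero.** Assume the same true mean decline of r SD in both arms, normal LS means, and 32 and 16 patients (the plan's evaluable numbers). The upper end, r = 0.72/1.36 = 0.53, uses the rise time from the DMD study in Protocol 4.2.2 ("time to stand from floor and PUL were -24.6±36.11 meters (mean±SD), -2.5±2.85 points, 0.72±1.36 seconds"). Smaller values are plausible because Protocol 4.1 says "The progression of BMD is slower and more variable than Duchenne Muscular Dystrophy (DMD"). With G = Φ(r√32) and P = Φ(4r):

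| r | Arms' changes of opposite sign: G(1−P) + (1−G)P | Placebo 95% CI covers zero: Φ(1.96−4r) − Φ(−1.96−4r) |
|---|---|---|
| 0 | 50% | 95% |
| 0.2 | 29% | 87% |
| 0.53 | 2% | 44% |

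Wherever the placebo interval for change covers zero, the reciprocal is unbounded.

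**The case against.** **Intent.** The sponsor may well have meant LS means of velocity level, since returning to the original scale makes sense only for levels. On that reading one clause is missing. But the text does not say so, and the reading rescues only rise from floor. The other two tests would still come out per stair and per metre. That lesser error is a constant rescaling, which leaves direction and relative precision intact.

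**Scope.** The step is exploratory, conditional and for display. No decision rests on it, and negative times would probably be noticed in the first output. This limits the consequence but does not make the formula right.

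**Wording.** For rise from floor, one over a change in velocity does carry units of seconds. The claim is that it is not the time taken to do the test.

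**Frequencies.** The 0.53 ratio is for time, not velocity, and comes from an open-label study of treated boys with no placebo arm. The percentages also ignore the trigger: a patient who loses ability on study has velocity zero, which pulls that arm's mean change downward, so the zero-decline row may overstate the risk. These points stand. The percentages show a range and do not predict this trial.

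**The repair.** In a repeated-measures fit with missing visits, the pooled mean baseline is ambiguous: over records or over patients. That is fair, and the fix must name the value.

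**Conclusion.** The step is wrong as written. Inverting an LS mean change in velocity gives neither a test time nor a change in test time. It has no value at zero change, and the arm difference reverses direction when the arms' changes have opposite signs. This follows from the algebra and needs no data. Even on the generous reading, the stair and 10 m results are off by factors of 4 and 10.

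The sizes shown (−10 or +100 against fractions of a second up to about 1 s; SE 17 against 0.33 s) rest on assumed velocities and SEs. The damage is confined to one exploratory presentation, triggered only when a patient cannot do a test or has the lowest grade. The velocity LS mean difference, its CI and p-value, and the primary and secondary analyses are unaffected.

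**What to change.** Replace the back-transformation paragraph in SAP 6.3.3 with the following:

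- V = LS mean change + b̄, where b̄ is the baseline velocity at which the LS means are evaluated. Name that value (for example, the pooled mean over patients in the model) and use the same number in both places.
- Report k/V, with k = 4 (stairs), 1 (rise from floor) and 10 (10 m).
- Δ = k/V_d − k/V_p.
- Var(Δ) = k² × [Var_d/V_d⁴ − 2Cov/(V_d²V_p²) + Var_p/V_p⁴].
- Label the result a time equivalent of mean velocity, not a mean time, because zero velocities are included.

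Baseline is already a covariate, so subtracting it from the outcome at every visit only shifts its coefficient by one. LS mean change plus b̄ therefore equals the LS mean of velocity at b̄, with the same SEs, covariance and treatment p-value; a single-visit ANCOVA on simulated data confirmed this. Modelling velocity at each visit with baseline as covariate is an equivalent route, though it changes the stated dependent variable.

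The cost is one SAP paragraph and a few lines of code, with no new data and, by the add-back route, no change to any model or endpoint. The drawback is that the result is still not a mean time, so the label has to say so.

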6.3.4. Measurement of Treatment Compliance

For each patient, the compliance will be calculated according to the following formula:

$$Compliance_{ji} = \frac{((number\ of\ days\ from\ last\ evaluation_{ji}*\ 2) - number\ of\ doses\ not\ taken_{ji})}{number\ of\ days\ from\ the\ last\ visit\ _{ji}*\ 2}$$

where j = patient 1, 2... and <math>i = visit 8, 9, 10 and 11.

The total compliance for each patient will be computed as the sum of the compliance at visit 8, 9, 10 and 11.

Total compliance will be summarized as <80% and 80-100%. The compliance will be also summarized as a continuous variable using descriptive statistics.

Treatment compliance will be calculated on ITT set using the information about doses not taken reported in the study diary or in the eCRF if no diary available.

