### 6 INVESTIGATIONAL PLAN

# 6.1 Description of Overall Study Design and Plan

This is a Phase 2, randomised, double-blind, placebo-controlled study. Ambulant patients who have provided written informed consent will undergo a 4-week screening period to determine eligibility for the study. Approximately 48 eligible patients will then be randomized in a 2:1 ratio to be treated with givinostat or placebo for a period of 12 months. The randomization process will be stratified by the factor related to concomitant steroid use at baseline (yes vs. no). Patients who complete the study (i.e. 12 months of treatment) will be asked to return for a follow-up visit 4 weeks after the end of treatment.

An overview of the study is provided in Figure 1.

Figure 1: Study Design

A total of 12 visits will take place during the study: Screening (V1, V2), Randomization (V3), Treatment (V4-V10), End of Study (V11) and Follow-up (V12). Visits during the treatment period will take place every 12 weeks except for the first 2 months, when they will occur every 2 weeks to allow close monitoring of hematological safety parameters. Patients may be evaluated more often if necessary, for safety reasons. Patients who discontinue the study treatment early will be asked to come in for an Early Withdrawal Visit within 4 weeks

17 June 2020 Page 43 of 110

after the last dose of study treatment. Patients who have ongoing AEs at discontinuation will be followed until resolution or stabilization.

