## 8.6 Treatment Accountability and Compliance

The study treatment packaging will be provided with tear-off labels; before treatment dispensation the tear-off label should be removed from the patient's pack by the Investigator and stuck on the appropriate drug accountability form.

At each dispensing visit, the patient will return all bottles previously received (used, partially used and unused) and receive a new supply of the study treatment.

Patient compliance will be evaluated through a patient diary indicating how many doses were effectively administered by the patient.

Drug accountability will be checked by Italfarmaco S.p.A. or its designee based on an accountability log completed by site staff and monitored by Italfarmaco S.p.A. or its designee.

The used, partially used, and unused bottles will be collected and sent back to Italfarmaco S.p.A. or their designee periodically or at the end of the study.

17 June 2020 Page 57 of 110

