# 9.1.2 Visit 3 - Randomization (Week 0)

Data collected at Visit 3 will represent baseline values for study endpoints.

At Visit 3, the following assessments will be performed:

- Review of eligibility criteria using the assessments done at screening.
- Prior and concomitant medications
- Physical examination
- Vital signs (blood pressure, heart rate and body temperature)
- Weight
- 12-lead ECG
- Blood collection for hematology and biomarker evaluation
- 6MWT
- Randomization and dispensation of study treatment
- AE assessments
- Patient diary dispensation

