### 9.1.6 Visit 7 (Week $8 \pm 3$ days)

At Visit 7, after 2 months of treatment (± 3 days), the assessments listed below will be performed.

- Concomitant medications
- Physical examination
- Vital signs (blood pressure, heart rate and body temperature)

17 June 2020 Page 65 of 110

- Weight
- 12-lead ECG
- Blood collection for:
  - hematology
  - blood chemistry
  - coagulation tests (prothrombin time [PT] and activated partial thromboplastin time [aPTT])
  - thyroid function tests (TSH, fT3, fT4)
- Urine analysis
- AE assessments

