## 9.1.7 Visit 8 (Week $12 \pm 7$ days)

The following assessments will be performed at Visit 8 ( $\pm$  3 days), after 3 months of treatment. Patients will be instructed to take the morning dose at the site in case of pre-dose PK analysis.

- Concomitant medications
- Physical examination
- Vital signs (blood pressure, heart rate and body temperature)
- Weight
- 12-lead ECG
- Blood collection for:
  - hematology
  - blood chemistry
  - coagulation tests (PT and aPTT)
  - thyroid function tests (TSH, fT3, fT4)
  - PK analysis
- Urine analysis
- 6MWT + MFM
- Muscle strength test (knee extension and elbow flexion by HHM)
- Time function tests
- Dispensation and accountability of study treatment
- Diary return and patient compliance
- AE assessments

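### Total compliance is a sum of four visit ratios, so a fully adherent completer scores 400% and fits neither of the SAP's two classes

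*SAP*

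**What the plan says.** SAP 6.3.4 gives a compliance ratio for Visits 8, 9, 10 and 11. The numerator is twice the number of days since the last evaluation, minus the doses not taken. The denominator is twice the number of days since the last visit. The section then says "The total compliance for each patient will be computed as the sum of the compliance at visit 8, 9, 10 and 11", and next "Total compliance will be summarized as <80% and 80-100" per cent. It adds that "The compliance will be also summarized as a continuous variable using descriptive statistics". Doses not taken come from the diary, or from the eCRF where there is no diary.

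The protocol gives no competing formula. Section 8.6 says only that "Patient compliance will be evaluated through a patient diary indicating how many doses were effectively administered by the patient". On timing, Protocol 9.1.2 lists "Patient diary dispensation" at Visit 3 (week 0), and "Diary return and patient compliance" first appears at Visit 8 (week 12, section 9.1.7). The scheduled visit before Visit 8 is Visit 7 at week 8 (section 9.1.6).

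**The concern.** Four ratios that each reach 1 cannot be added and then read against a scale that stops at 100%. No text in the protocol or the SAP divides the sum by four, pools the doses or supplies a class above 100%.

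Programmed as written, the two-class table would leave any completer with more than 25% mean adherence unclassified. It would also label very poor adherence as 80–100%. If most completers take more than a quarter of their doses, which is an assumption because the documents give no adherence data, most of them would have no class.

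A second ambiguity sits in the same formula: the numerator and the denominator name different starting points, and the SAP does not say whether they are the same date.

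**Working it through.** **Inputs**

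- Two doses a day (Protocol 8.2.2; the factor 2 in the SAP formula).
- Visits 3, 8, 9, 10 and 11 at weeks 0, 12, 24, 36 and 48 (Protocol 9.1.2 and 9.1.7 to 9.1.10), so four nominal diary intervals of 12 × 7 = 84 days.
- Visit 7 at week 8 (Protocol 9.1.6), so 28 days before Visit 8.

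**Reading 1: same interval in numerator and denominator**

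For interval i of length d_i days, ratio_i = (2d_i − missed_i) / (2d_i), which is at most 1. The total is therefore at most 4.00, or 400%. A patient who misses nothing scores exactly 400% whatever the visit windows, because each ratio is scaled by its own interval.

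The total is four times the mean ratio, so for a completer:

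- a total of 80% corresponds to mean adherence of 80/4 = 20%;
- a total of 100% corresponds to mean adherence of 100/4 = 25%.

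With nominal intervals, 84 × 2 = 168 doses are due per interval and 4 × 168 = 672 overall. The total is then doses taken / 168.

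| Doses taken of 672 | True adherence | Total as defined | Class assigned |
|---|---|---|---|
| 672 | 100% | 400% | none |
| 538 | 80.1% | 320.2% | none |
| 336 | 50% | 200% | none |
| 169 | 25.1% | 100.6% | none |
| 168 | 25.0% | 100% | 80–100% |
| 135 | 20.1% | 80.4% | 80–100% |
| 134 | 19.9% | 79.8% | <80% |

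At these nominal intervals, anyone taking 169 to 672 doses has no class. The dose counts move with the ±7-day windows; the 20% and 25% limits on the mean ratio do not.

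**Reading 2: different intervals at Visit 8**

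If the last evaluation is the diary start at Visit 3 and the last visit is Visit 7, a fully adherent patient has (84 × 2) / (28 × 2) = 168/56 = 3.0 at Visit 8. The total is 3 + 1 + 1 + 1 = 6, or 600%. At uniform adherence a, the total is 3a + 3a = 6a, so the 80–100% label covers a = 80/6 to 100/6, that is 13.3% to 16.7%.

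**Other assignments for a fully adherent completer**

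- Numerator from Visit 7, denominator from Visit 3: 28/84 + 3 = 3.33, or 333%.
- Both from Visit 7: 400%.

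Every reading exceeds 100%.

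**Measures that do fit the classes**

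The mean of the four ratios, or pooled doses taken over doses due, gives 100% for the fully adherent completer and 80% for one who misses 20% of doses in each interval. The SAP states neither.

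**Missing visits**

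The SAP does not say how a missing visit enters the sum. If it is left out (assumption), a fully adherent patient with k visit values scores k × 100%. One value gives 100% and a class; two or more give 200% or higher and none.

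**The case against.** The strongest reply is that the 80–100% class makes the intended scale obvious, so the word sum is a slip for a mean or pooled value, and an output table with nearly everyone unclassified would be noticed at once. That is probably how the text arose, but it does not repair it. Where this SAP wants an average it says so: section 6.3.2.3 divides the sum over four fields by four for centralised and regenerative fibres, and section 6.3.1 uses a mean of available fields for fibrosis. Section 6.3.4 gives no divisor. The mean and the pooled ratio can also differ when intervals are unequal, so a programmer would have to choose a rule that the plan does not state.

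A second reply is that the 600% figure is only one nominal reading and that the reverse assignment gives 333%, less than 400%. The arithmetic is right. However, the reverse needs the last evaluation to mean Visit 7 and the last visit to mean Visit 3, which neither the wording nor the diary schedule supports. The conclusion does not depend on which reading is chosen.

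The third reply stands: no efficacy or safety model in the SAP uses total compliance. The per-protocol exclusions are in a separate document that was not available, so no effect there can be shown. If the continuous summary refers to the visit ratios, the summing does not touch it.

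**Conclusion.** The concern holds. As written, total compliance for a completer runs to 400% when both day counts cover the same interval, while its classes stop at 100%. Mean adherence above 25% then has no class and 20–25% is labelled 80–100%. With the Visit 8 day counts taken from Visit 3 and Visit 7, the maximum is 600% and the mislabelled band at uniform adherence is 13.3–16.7%. The dose counts assume nominal 84-day intervals; the mismatch itself does not.

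Severity is minor. The error affects one descriptive table, and no effect on the primary analysis or the per-protocol set is shown.

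**What to change.** In SAP 6.3.4, replace the sum with a named measure on a 0–100% scale. The preferred form is the pooled ratio

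100 × (total scheduled doses − total doses not taken) / total scheduled doses,

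taken over the intervals Visit 3 to 8, 8 to 9, 9 to 10 and 10 to 11. A mean of the available visit ratios would also restore the scale and equals the pooled ratio when the four intervals are equal.

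Use one day count in numerator and denominator, defined as days since the previous diary visit (since Visit 3 for Visit 8). Keep the <80% and 80–100% classes on the new measure, and say how a missing visit is handled. The same edit could state whether days of temporary interruption, and days between the last dose and an early withdrawal visit, count as scheduled; the current formula leaves both open.

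The cost is SAP wording only, with no new data.
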